2. Objectives (include all primary and secondary objectives)

Primary Aim 1. Examine whether individuals who are randomly assigned to SUVO 20mg (oral) will be less likely to test positive for (i) cocaine and (ii) non-prescribed opioids on urine drug screens (UDS) and will self-report lower opioid and cocaine craving, relative to those receiving placebo.

Date: 09/19/2024

Principal Investigator: [name].

Application Number: IRB00341328

Secondary Aim 1. Examine whether, relative to placebo, SUVO 20mg will improve self-reported sleep quality and total sleep time, as assessed via a sleep diary and an actigraph-like device, and will reduce self-reported insomnia symptoms and wake after sleep onset (WASO).

Secondary Aim 2. Given previous work suggesting that Suvorexant has a good safety profile among patients using opioids and patients using cocaine, a secondary aim will test no between-group differences in the rate of adverse events between individuals assigned to Suvorexant and placebo.

Secondary Aim 3. Examine whether SUVO 20mg will be associated with lower stress reactivity, lower self-reported stress and negative affect, and greater positive affect, relative to placebo.

3. Background (briefly describe pre-clinical and clinical data, current experience with procedures, drug or device, and any other relevant information to justify the research)

Opioid/stimulant co-use is a public health crisis that is increasing in prevalence (Goodwin et al., 2021) and directly contributing to increases in overdose deaths and disproportionately impacting minority individuals (Townsend et al., 2022). Individuals engaged in opioid/stimulant co-use face a greater risk of treatment discontinuation and continued substance use (Levin et al., 2015).

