Study Overview: Participants who are in methadone or buprenorphine treatment for OUD and are using cocaine will be recruited from the community to visit the clinic twice weekly and provide urine tests that will be analyzed for evidence of recent drug use and complete self-reported measures. All participants will be randomized to receive double-blinded doses of suvorexant (20mg, oral, QD) or placebo, which will be dispensed in blister packages for 28-30 days. Medication will be over-encapsulated and will include either 10mg SUVO or placebo. Participants will be expected to take 2 capsules each night and will be informed they can reduce their dose to 1 capsule per night if desired (these data will be documented as a secondary outcome).

Recruitment: Participants will be recruited from the community using social media advertisements, flyers, and newspaper advertisements. Recruitment will also include review of clinical records of individuals who are not clinical patients of the PI or co-investigators prior to their consent at Man Alive. At ATS, recruitment will include referral of individuals specifically for research purposes by treating clinicians not on the study team and recruitment of individuals who are patients of the study co-investigators. Interested individuals will complete a brief screening to determine initial eligibility before completing a full eligibility screen.

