Participants will be blinded to whether they received SUVO vs. placebo. This is meant to enhance study rigor and control for expectancy effects.

e. Justification of why participants will not receive routine care or will have current therapy stopped.

There is no current routine care for stimulant use disorder. Participants will not be removed from routine care and will continue participating in their treatment for OUD as indicated.

f. Justification for inclusion of a placebo or non-treatment group.

Inclusion of a placebo group will be necessary to determine if SUVO is efficacious in improving outcomes for patients receiving treatment for OUD and using cocaine.

g. Definition of treatment failure or participant removal criteria.

Participants will be removed from the study if they opt out or if the medical team determines it is not safe to continue in the study or if they request to discharge from the study. Participants who become pregnant, are incarcerated or hospitalized for ≥ 7 days, end their OUD treatment, or rescind consent/ask to be discharged will be removed from the study. Additional stopping rules will include not abiding by study policies and procedures, or engaging in behaviors towards staff or other participants that are abusive. Finally, development of an intercurrent illness or condition that changes the participant's risk profile may result in a medically-related discharge from the study.

Date: 09/19/2024

Principal Investigator: [name].

Application Number: IRB00341328

h. Description of what happens to participants receiving therapy when study ends or if a participant's participation in the study ends prematurely.

Participants will continue to receive their clinically-indicated care for OUD treatment.

Participants will be able to request a suvorexant prescription from their PCP if interested in continuing with the study medication after study completion.

i. If biological materials are involved, please describe all the experimental procedures and analyses in which they will be used.

Urine drug screens will be used as an outcome in this analysis. Urine drug screens will be taken at each visit using biochemical urine panel dip stick tests. The research coordinator will record the result of the urine drug screen. Urine specimens will be stored for future research.

5. Inclusion/Exclusion Criteria

Inclusion criteria:

- 1) Ages 18-65,
- 2) Meet DSM-5 criteria for stimulant use disorder,

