Secondary Aim 1 and 3. To examine whether SUVO 20 mg improves 1) insomnia symptoms, 2) indices of sleep continuity, and 3) co-occurring affective symptoms relative to placebo, a series of mixed effects models will be conducted. For each model, we will include main effects of timepoint and medication group, as well as an interaction term. If the two treatment groups are systematically different on demographic or use characteristics at baseline, these measures will be included as covariates in the analysis. Models will involve a random intercept. Mixed effects models will also be used to compare drug cue reactivity at baseline and during the final week.

Secondary Aim 2. To compare SUVO 20mg to placebo on number of adverse events experienced, t-tests will be used.

Power analysis and sample size. A sample size of 40 will be used in this study. For all aims, we are sufficiently powered to detect moderate-to-strong effect, which has been observed in

Date: 09/19/2024

Principal Investigator: [name].

Application Number: IRB00341328

previous studies (e.g., Huhn et al., 2022). Due to our smaller sample size, effect size measures will also be considered.

All analyses will be conducted in SPSS and R. Two-tailed tests and an alpha level of .05 will be used.

d. Early stopping rules.

Participants will discontinue the study if the medical team determines it is not safe to continue in the study or if they request to discharge from the study. Additional stopping rules will include not abiding by study policies and procedures, or engaging in behaviors towards staff or other participants that are abusive. Finally, development of an intercurrent illness or condition that changes the participant's risk profile may result in a medically-related discharge from the study.

8. Risks

a. Medical risks, listing all procedures, their major and minor risks and expected frequency.

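### Secondary Aim 2 asks about the rate of adverse events but t-tests the number, ignoring time on study, so unequal early exit can hide or create a safety difference

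*Combined protocol and SAP*

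**What the plan says.** All references are to the combined protocol and SAP.

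- **Section 2, Secondary Aim 2:** the aim is to "test no between-group differences in the rate of adverse events between individuals assigned to Suvorexant and placebo".
- **Section 7c, Secondary Aim 2:** the whole analysis is one sentence: "To compare SUVO 20mg to placebo on number of adverse events experienced, t-tests will be used". The general rule that follows is "Two-tailed tests and an alpha level of .05 will be used".
- **Section 7b:** adverse events are asked about at each visit and can be reported through a contact number. Start and stop times are recorded.
- **Section 4a, Final/Exit visit:** the last visit falls at day 28-30 (+7 days) or on whatever day participation ends.
- **Section 4g:** "Participants will be removed from the study if they opt out or if the medical team determines it is not safe to continue". It also lists pregnancy, incarceration or hospitalisation of 7 days or more, leaving OUD treatment and withdrawn consent. Sections 4g and 7d both add breaches of study policy and intercurrent illness.

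No section defines the rate, gives an exposure window or an offset, or says how the events of someone who leaves early enter the comparison.

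**The concern.** A rate has time in its denominator; a t-test on a number of events does not. The two agree only if follow-up is the same length for everyone, or at least has the same average length in both arms. Several of the listed exit routes are safety-driven, so the average could differ by arm.

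Suppose suvorexant truly causes more events and its participants also leave sooner. The shorter observation then cancels part of the excess and moves the result toward no difference, which is what Aim 2 expects to find. If placebo participants leave sooner, suvorexant can appear to cause events that it does not. In a pilot meant to inform whether the drug is worth scaling up, either error would carry over into the safety summary.

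**Working it through.** **1. The plan's own figure.** Section 7c states "A sample size of 40 will be used in this study" and "we are sufficiently powered to detect moderate-to-strong effect", with no event rate, SD, dropout rate or power figure, so nothing specific to Aim 2 can be reproduced. Assuming 20 per arm (the allocation ratio is not stated) and two-sided 0.05, a t-test has 34% power at d = 0.5 and 69% at d = 0.8. The effect detectable with 80% power is d = 0.91.

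**2. Assumptions for the check (none is in the documents).** 20 per arm; 4 weeks of planned follow-up; placebo rate 0.5 events per week; gamma-Poisson counts with shape 2, so a full-follow-up mean μ has variance μ + μ²/2. Leavers exit uniformly between weeks 0.3 and 2.5 (mean 1.4), unrelated to their events.

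**3. Mean follow-up and expected counts.** With dropout share p, mean follow-up is 4(1 − p) + 1.4p weeks. At 10% this is 3.60 + 0.14 = 3.74; at 20%, 3.20 + 0.28 = 3.48; at 30%, 2.80 + 0.42 = 3.22; at 50%, 2.00 + 0.70 = 2.70.

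For a true rate ratio of 2 (suvorexant 1.0 per week), placebo mean count is 0.5 × 3.74 = 1.87 at 10% dropout:

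| Dropout, suvorexant vs placebo | Mean counts | Difference | Count ratio |
|---|---|---|---|
| none | 4.00 vs 2.00 | 2.00 | 2.00 |
| 20% vs 10% | 3.48 vs 1.87 | 1.61 | 1.86 |
| 30% vs 10% | 3.22 vs 1.87 | 1.35 | 1.72 |
| 50% vs 10% | 2.70 vs 1.87 | 0.83 | 1.44 |

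For a true ratio of 1.5, the difference falls from 3.00 − 2.00 = 1.00 to 0.75 × 2.70 − 0.5 × 3.74 = 2.025 − 1.870 = 0.155 at 50% vs 10%.

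**4. Hand check of one power figure.** With ratio 2 and no dropout, the variances are 4 + 16/2 = 12 and 2 + 4/2 = 4. SE = √(12/20 + 4/20) = 0.894, and 2.00/0.894 = 2.24. Normal-approximation power is Φ(2.24 − 1.96) = Φ(0.28) = 0.61, which agrees with the simulated 61%.

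**5. Simulated rejection rates** (at least 2,000 trials per scenario; runs differ by a point or so):

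| Dropout gap | t-test power, ratio 2 | Rate model power, ratio 2 | t-test false positives, ratio 1 |
|---|---|---|---|
| none | 61% | about 60% | – |
| 20% vs 10% | 43% | about 60% | 6% |
| 30% vs 10% | 32% | about 60% | 7% |
| 50% vs 10% | 15% | about 60% | 15% |

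The rate model is quasi-Poisson with log follow-up as offset; its false-positive rate at the widest gap is about 6%. Equal dropout in both arms leaves the t-test at 4% to 5%.

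**6. A different exit pattern.** Let leavers exit uniformly over 28 days, with 2 placebo events per 28 days, Poisson counts and a true ratio of 1.5. Count t-test power is 40% with equal dropout, 15% at 40% vs 10%, and 9% at 50% vs 10%. The person-time analysis keeps 41% to 46%. With strongly overdispersed counts (shape 1), false positives at 40% vs 10% are only 6% to 7%.

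**7. Events that trigger exit.** Keep the rates in step 2, but let each event cause exit with probability 30% on suvorexant and 5% on placebo (assumed).

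- *Equal true rates:* suvorexant leavers average 1.8 events and completers 1.1. False positives are about 15% for the t-test and 2% for the rate model.
- *True ratio 2:* power is about 6% for the t-test and 26% for the rate model (22% in another run), and the rate model estimates a ratio of about 1.7.
- *True ratio 2, exit probability 30% in both arms:* power is 27% for the t-test and 20% for the rate model.

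**The case against.** The strongest reply has four parts.

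*Leavers need not have few events.* A reader might infer that anyone who exits early contributes a low count. The documents do not support that: someone removed on safety grounds has typically had at least one event, and in step 7 leavers have more than completers. This stands. It changes the mechanism but does not rescue the count test, which still performs badly when event-driven exit is more common on suvorexant.

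*The rate model is not a full repair.* This also stands. It holds about 60% power only when exit is unrelated to events, and it has no advantage when exit is equally event-sensitive in both arms.

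*Poor tolerance need not end observation.* Sections 4a and 8b let participants take one capsule, and section 8b lets them stop medication. A contact number exists, and a phone call after exit asks about symptom changes. These soften the problem, but nothing says they restore event follow-up to day 28. They also mean that days on study measure observation time, not drug exposure.

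*The scale is modest.* This is a secondary aim in a 40-person pilot, and "rate" may be meant loosely. If it means the proportion with an event, however, a t-test on a number does not match that either.

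**Conclusion.** The point holds: the aim and its analysis measure different things, follow-up can vary, and nothing in the plan adjusts for it. The direction of bias depends on which arm loses more observation time; masking of a real excess is the larger worry.

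The size is conditional on assumed event and dropout rates. Under the step 2 assumptions, a 10-point dropout gap costs meaningful power (61% to about 43%) but barely moves the false-positive rate. A 40-point gap cuts power to about 15% and raises false positives to about 15%. A reader might infer that the planned safety comparison is bound to mislead, or that a gap of 50% vs 10% is to be expected. The documents give no dropout figure for either arm, and equal dropout does not inflate false positives, so neither inference is supported. The change is worth making because it is cheap, not because serious bias is certain.

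**What to change.** In section 7c, replace the t-test on counts with a comparison of events per person-week on study: a negative binomial or over-dispersed Poisson model with log days of follow-up as offset. Report the rate ratio with a 95% confidence interval, and use the same definition of rate in section 2. The interval also shows how large a difference the data leave open, which a non-significant test in 40 people would not.

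Beside it, show for each arm the total follow-up time, the number who left because of an adverse event, and the proportion with at least one event (or time to first event). These rows are needed because person-time alone does not fully correct for exit driven by events.

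The cost is a sentence or two in section 7c, a slightly less familiar model and a few more summary rows. Event dates are already recorded, exit dates will be known, and R is already planned, so no new data, visits or participants are required.

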Suvorexant for Opioid/Stimulant Co-use

NCT05546515

9/19/2024

JHM IRB - eForm A – Protocol

- Use the section headings to write the JHM IRB eForm A, inserting the appropriate material in each. If a section is not applicable, leave heading in and insert N/A.
- When submitting JHM IRB eForm A (new or revised), enter the date submitted to the field at the top of JHM IRB eForm A.

1. Abstract

The opioid epidemic has led to an unprecedented rise in opioid use disorder (OUD) cases and overdose deaths. In recent years, these increases have been accompanied by a rise in opioid/stimulant co-use, an issue that has existed for decades and for which no effective treatment has ever been identified. Current increases in opioid overdose deaths are now largely driven by stimulant co-use. Thus, innovative treatments that are safe and effective among patients co-using opioids and stimulants are urgently needed. Suvorexant (SUVO) is an FDA-approved medication used to treat insomnia. SUVO interacts with the brains reward system in such a way that it may reduce craving for stimulants in persons using opioids, and we recently also found that SUVO reduced craving and increased total sleep time among individuals who were withdrawing from opioids. That study also showed that SUVO was extremely safe and well-tolerated in persons using opioids.

This between-subjects, double-blinded, randomized controlled pilot study will recruit patients who are receiving methadone or buprenorphine treatment for OUD and are using cocaine. Participants will be randomly assigned to receive 28-30-days of SUVO or placebo. They will visit the clinic regularly to provide urine drug screens and complete questionnaires and will wear a device that can measure their sleep parameters. We expect that relative to persons who receive placebo, individuals who receive SUVO will 1) be less likely to screen positive for cocaine and/or opioids on urine drug screens, 2) will report lower drug craving, 3) will have better sleep continuity (i.e., longer total sleep time, shorter wake after sleep onset, and greater self-reported sleep quality, and 4) will report overall lower stress and better mood than persons who receive placebo. We also expect that patients will not have side effects from SUVO. These preliminary data will inform whether this FDA-approved medication may help patients stop co-using opioids and stimulants, which can be scaled up to reduce public health consequences related to co-use.

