Weekly visits. Participants will complete visits twice weekly during the study period. At these visits, participants will be asked to complete a urine drug screen and self-report measures as described below. Medication will be dispensed once weekly during these visits.

Final/Exit visit. The final study visit will be collected at day 28-30 (+7 days) or the final day of study participation. At their final visit, participants will complete a urine drug screen and self-report measures, and tasks. Participants will be able to request SUVO prescriptions from their provider if desired and all participants can request study drug unblinding after data collection is closed.

Follow-up phone visit: Participants will be contacted via phone after the final/exit visit. Information will be collected on their experience during the study, any changes in symptoms following study exit, treatment plans going forward, and other feedback regarding the study.

Sleep diaries: To facilitate scoring of actigraphy data, participants will be asked to complete nightly sleep diaries.

The following study Measures may be used:

- Mini-International Neuropsychiatric Interview (M.I.N.I.): The MINI is a semi-structured interview that will be used to assess presence of stimulant use disorder.
- Addiction Severity Index: The ASI will be used to collect information related to severity of recent substance use disorder
- Columbia Suicide Severity Rating Scale: The C-SSRS is the standard for assessing present risk for suicidality. It will be administered at screening and end of study, and point prevalence during the study as indicated.
- Demographic questionnaire. This will ask participants basic demographic information (e.g., gender, age, race, ethnicity, employment status, etc.)
- Medical History: A self-reported medical history will be collected to determine eligibility for suvorexant administration.
- Assessment of previous medication administration: Participants will be asked whether they have ever received a number of different medications, either illicitly or through a prescription.
- Medication expectancy questionnaire. Participants will be asked to rate how much they expect to like the study drug, as well as how much they expect the study drug to help improve various symptoms (i.e., opioid use, cocaine use, sleep, stress).

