Application Number: IRB00341328

is asleep, 2) wake after sleep onset (WASO), or the total number of minutes that an individual is awake after sleep onset and prior to awakening, and 3) subjective sleep quality.

Co-occurring affective symptoms. Participants will be assessed for positive and negative affect using the PANAS. Participants will report perceived stress using the Perceived Stress Scale (PSS) is a 10-item measure of perceived stress. Items are rated on a five-point scale.

Abuse Liability Assessments (i.e., Medication Satisfaction Questionnaire). Participants will be asked to complete abuse liability measures. Participants will also be assessed for adverse events and serious adverse events in each visits. The abuse liability of the blinded study drug will be assessed by asking participants to rate “drug effects”, “good effects”, and “bad effects”, on a 0-100 point VAS, with 0 being “None” and 100 being “Extremely”. Participants will also report the perceived street value of the study drug. These subjective drug effect ratings are considered by the FDA to be the gold standard for assessing abuse liability.

Adverse events We will follow standard FDA guidelines regarding adverse events. Participants will be able to self-report adverse events via a study contact number. Events will be documented on a standardized form that adheres to FDA standards for adverse event reporting (e.g., event, system affected, start and stop date/time, perceived relationship to the study, severity, expectedness).

c. Statistical plan including sample size justification and interim data analysis.

Primary Aim 1. To examine whether SUVO 20mg reduces opioid and cocaine use and craving relative to placebo, a series of mixed models will be conducted. For analyses with a binary outcome (i.e., use at each assessment), generalized logistic models will be used, and for analyses with a continuous outcome (i.e., craving), linear mixed models will be used. Mixed effects models will also be used to compare drug cue reactivity at baseline and during the final week. For each model, we will include main effects of timepoint and medication group, as well as an interaction term. If the two treatment groups are systematically different on demographic or use characteristics at baseline, these measures will be included as covariates in the analysis. Models will involve a random intercept.

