Suvorexant is a Schedule IV dual orexin receptor antagonist (DORA) that is FDA-approved for the treatment of insomnia. Suvorexant is 82% bioavailable and has a Tmax of 2 hours. Tmax can be delayed by food though this does not impact the Cmax. It is extensively metabolized by the liver through CYP3A enzymes. The elimination half-life is 12 hours, and it is excreted through both renal (23% unchanged) and fecal (66%) means. Suvorexant is contraindicated with other CNS depressants and alcohol and strong CYP3A inhibitors. It is rated pregnancy category C, indicating insufficient data available to make determination for human subjects. Suvorexant is contraindicated in patients with narcolepsy, patients with recent suicidal behavior, or patients with severe hepatic impairment. There is no evidence of potential overdose and a toxic dose has not been established. Clinical trials that administered up to 240mg of suvorexant reported no overdose effects, though there was a dose-dependent increase in the frequency and duration of next day somnolence. As per product label, most common side effects are sleepiness/drowsiness (7% of people), headache (7%), dizziness (3%), diarrhea (2%), dry mouth (2%), upper respiratory infection (2%), abnormal dreams (2%), and cough (2%). Serious adverse effects include sleep paralysis (7%), somnolence (7%), and worsening of depression or suicidal ideation.

b. Steps taken to minimize the risks.

Individuals with medical or psychiatric contraindications and/or individuals who are taking exclusionary medications (including CNS depressants such as benzodiazepines or other sleep medications), individuals with co-occurring moderate or severe substance use disorder, those with current and major psychiatric illness (e.g., bipolar disorder) or past 30-day suicidal behaviors are excluded for participating. Participants will be provided the maximum FDA-approved dose (20mg). All medication will be dispensed in two (10mg) capsules and participants will be informed they can refuse reduce from 2 to 1 capsule or stop taking medication at any point and we will track participant acceptance (e.g., in terms of adherence with dosing schedule) of the medication as part of the study. Given that suvorexant can cause next-day drowsiness, participants will be explicitly instructed not to drive or operate heavy machinery under any circumstances within 8 hours of taking suvorexant for the first time, or if they continue to feel

Date: 09/19/2024

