Principal Investigator: [name].

Application Number: IRB00341328

drowsy or have cognitive difficulties after 8 hours post suvorexant dosing. Participants will also be instructed to contact the study team if drowsiness or cognitive difficulties persist for longer than 8 hours after dosing. All participants will be asked to plan alternative transportation strategies if needed.

Participant adverse events (AEs) will be monitored and documented. Participants will be provided with a study contact number in case they experience an adverse event outside of a typical study visit. Events will be documented on a standardized form that adheres to FDA standards for adverse event reporting (e.g., event, system affected, start and stop date/time, perceived relationship to the study, severity, expectedness). We will also document whether concomitant medications were self-administered in response to the event (and the associated medication, dose, route, start and stop date/time, and outcome), whether the event resolved by study discharge, and whether the event met the criteria for a serious adverse event.

All events will be documented by trained staff members and will be disclosed to the study PIs and the study physician daily via daily memos (confidential emails that are sent each night to the study team via secure email system). Events will be discussed by the team at weekly study meetings or more frequently as needed. Any event that exceeds an *a priori* safety threshold, that is unexpected or of unexpected severity, or for which the participant expresses concern, will result in the staff member contacting a medical team member immediately via phone for a consultation. Staff will be instructed to document all adverse reports.

c. Plan for reporting unanticipated problems or study deviations.

All SAEs will be reported to the JHM IRB within 3 working days after a study PI learns of the event. In addition, the study PI will notify the study co-investigators. The PI will coordinate dissemination of subsequent information obtained relating to the death (e.g., autopsy report, hospital records, toxicological analyses).

The Johns Hopkins IRB will be provided with an annual summary of AEs and SAEs as part of the continuing review. If any SAEs requires a change to the protocol or consent form, the PI will make those changes promptly and submit the revised documents to the JHM IRB and appropriate other agencies.

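### Secondary Aim 2 seeks to show no adverse-event difference, but a non-significant t-test on event counts in 40 people cannot, and 7c plans no arm comparison of the serious harms named in 8a

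*Combined protocol and SAP*

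**What the plan says.** Section 2 (Secondary Aim 2) states that "a secondary aim will test no between-group differences in the rate of adverse events". The Abstract adds: "We also expect that patients will not have side effects from SUVO". The whole analysis for this aim, in 7c, is: "To compare SUVO 20mg to placebo on number of adverse events experienced, t-tests will be used". No margin is given for how large a difference would still count as none.

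Section 8a states: "Serious adverse effects include sleep paralysis (7%), somnolence (7%), and worsening of depression or suicidal ideation".

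The data for a finer comparison are already gathered:

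- The adverse-event form in 7b records "event, system affected, start and stop date/time, perceived relationship to the study, severity, expectedness".
- Section 8b adds "whether the event resolved by study discharge, and whether the event met the criteria for a serious adverse event".
- Section 7b says: "Participants will also be assessed for adverse events and serious adverse events in each visits".
- For the C-SSRS, section 4a says: "It will be administered at screening and end of study, and point prevalence during the study as indicated".

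The C-SSRS is not an outcome in 7a or 7b and has no analysis in 7c. The nearest mood analysis is the mixed model for affect and perceived stress under Secondary Aim 3. It compares average scores, not the number of people whose depression worsened.

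**The concern.** There are two linked problems.

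The first is interpretation. An aim worded as showing no difference is paired with an ordinary difference test and no margin. Followed literally, a p-value above 0.05 meets the aim. In a trial this small that result is likely whether or not the drug causes harm, and the stated expectation of no side effects makes it easy to accept as confirmation.

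The second is content. A count treats a cough and a disabling episode of drowsiness as one event each. Whatever the count shows, it does not tell a reader how many people in each arm had somnolence, sleep paralysis, worsening depression or suicidal ideation. Those are the facts a later, larger trial in people taking methadone or buprenorphine would need from this pilot.

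**Working it through.** **Inputs from the plan.** Total sample 40, two-sided alpha 0.05 (7c). Somnolence 7% and sleep paralysis 7% (8a); no rate is given for worsening depression or suicidal ideation.

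**Assumptions.** 1:1 allocation, so 20 per arm (the ratio is not stated), and no dropout.

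**The plan's own figure.** Section 7c says 40 is enough for a moderate-to-strong effect on all aims. This cannot be reproduced, because no power level, effect size or standard deviation is given.

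**Step 1. What a non-significant t-test can show.**

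- Power with 20 per arm, by the noncentral t distribution: 34% at d = 0.5 and 69% at d = 0.8.
- 80% power needs d of about 0.91. The normal approximation gives (1.96 + 0.84) × √(2/20) = 0.89.
- Half-width of the 95% CI for the difference in mean counts: t(0.975; 38 df) × √(2/20) = 2.024 × 0.316 = 0.64 SD. Even an observed difference of exactly zero leaves true differences up to about 0.64 SD in either direction.

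**Step 2. What the trial can say about one named harm at 7%.**

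- Expected affected on suvorexant: 20 × 0.07 = 1.4.
- Probability of no case: 0.93^20 = 0.234, so 23% of trials would see none.
- Exact two-sided 95% upper limit after 0/20: 1 − 0.025^(1/20) = 0.168, or about 17%. That is more than twice the 7% in 8a.

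**Step 3. What the added table would show.** Risk differences, suvorexant minus placebo, with Newcombe score 95% intervals:

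| Suvorexant | Placebo | Difference (points) | 95% CI (points) |
|---|---|---|---|
| 0/20 | 0/20 | 0 | −16 to 16 |
| 1/20 | 0/20 | 5 | −12 to 24 |
| 2/20 | 1/20 | 5 | −15 to 26 |
| 6/20 | 1/20 | 25 | 1 to 47 |

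**Step 4. Whether to test each harm formally.** No. At 7% against an assumed 3% on placebo, Fisher's exact test has 0.6% power. Against 0/20, the smallest split reaching p < 0.05 is 5/20 (p = 0.047). The table is therefore for estimation.

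**The case against.** **The analysis matches the aim as written.** Section 2 speaks of the rate of adverse events, and 7c compares the number of events. Nothing in the plan forbids a by-type table, and 7b says FDA guidelines on adverse events will be followed. This is fair, and it is why the priority is low. But no by-arm table is planned either. The monitoring and IRB reporting in 8b and 8c protect individuals and do not compare the arms.

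**The plan does not rely on p-values alone.** Section 7c adds that effect sizes will be considered because the sample is small. That stands as a sign of good intent, but it sets no rule for Aim 2 and names no harm. Nor does any section say outright that a non-significant count will be declared proof of safety. The risk comes from the wording of the aim combined with the absence of a margin.

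**At the documented rate the table detects nothing.** Correct, as Step 4 shows. The gain is that readers see what cannot be ruled out.

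**The 7% for sleep paralysis looks doubtful.** It is missing from the list of common effects in 8a, which runs down to 2%. If the true rate were 2%, the chance of no case in 20 would rise to 0.98^20 = 67%. The 17% upper limit after 0/20 does not depend on the rate.

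**A reader might go further and infer that the total count hides a specific harm.** The documents do not support this in general. Masking needs somnolence of around 20–30%, three to four times the rate in 8a, and equal rates of all other events in both arms. The other common effects in 8a sum to 7 + 3 + 2 + 2 + 2 + 2 + 2 = 20%, or 0.2 events per person. If that applies on suvorexant and half of it (0.1, assumed) on placebo, with somnolence at 7% against 3%, simulation shows the t-test on counts detecting an excess in about 15% of trials. A somnolence interval excludes zero in under 1%. Where a drug raises several effects at once, pooling helps.

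**Conclusion.** The point holds as a cheap, low-priority improvement. With 20 per arm assumed and no dropout, a non-significant t-test on event counts cannot show that the arms do not differ: power is 34% at d = 0.5, and the interval reaches 0.64 SD either side of the estimate. The count also leaves the harms that 8a calls serious without any arm comparison. At 7%, nearly a quarter of trials would see no case on suvorexant, and zero cases would still be compatible with about 17%.

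Two stronger conclusions a reader might draw do not follow. One is that the count comparison should become descriptive only. It is the only pre-specified test for Aim 2 and can be the more sensitive measure when several effects rise together. The other is that recurrent episodes should be counted once per participant. The plan does not say how separate episodes enter the count, but collapsing them discards burden, and nothing in the documents makes that the right trade-off.

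**What to change.** In 7c, under Secondary Aim 2:

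1. Keep the comparison of event counts. Report the between-arm difference with a 95% CI, and state that a non-significant result will not be read as showing no difference.
2. Add one table giving, per arm, the number and percentage of participants with each of the following:
   - somnolence or next-day drowsiness;
   - sleep paralysis;
   - worsening depression (adverse-event form);
   - new or worse suicidal ideation (adverse-event form plus C-SSRS, screening to exit);
   - any moderate-or-worse event;
   - any serious event.
3. Give each row a risk difference with a score or exact 95% CI, labelled as an estimate and not a confirmatory test.

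The cost is a few sentences in the plan and one table. No participants, visits or instruments are added, because the adverse-event form and C-SSRS already supply the data. The downside is several more wide-interval safety estimates, which need to be presented as such.
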